**TRIAL SUMMARY**

Full study title	Fibre-optic guided tracheal intubation through supraglottic airway devices – a randomised comparison between I-gel® and the LMA Protector™	
Short study title	Fibre-optic guided tracheal intubation through SAD's	
Trial Design	Multi – centre randomised	
Trial Participants	All patients aged 18 and above, presenting for elective surgical procedure where a supraglottic airway device can be used.	
Planned Sample Size	180 across 2 sites	
Follow up duration	0 months	
Planned Trial Period	12-14months	
	Objectives	Outcome Measures
Primary	Successful tracheal intubation	Time from insertion of from insertion of scope till end-tidal CO 2
Secondary	Successful placement of supra-glottic airway device	Number of attempts Time taken to insert supra-glottic airway device

**Key Words:** Intubation; tracheal, airway device; supra-glottic airway device, fibrooptic scope.

**TRIAL FLOW CHART**

*Figure 1: Flow of participants through the study*

## SCHEDULE OF OBSERVATIONS

Table 1: Schedule of measures

SAD insertion time (from insertion into the mouth of until 1st capnography trace is obtained)
SAD insertion score: 1-easy, 2 – mild difficulties, 3 – difficult, 4 - failure
SAD insertion attempts
Leak pressure: pressure at which audible leak starts, set flow at 6L/ mins and increase the APL valve pressure.
FOI: View grade grade I – full view of the vocal cord, II – partial view of the vocal cords & arytenoids, III – epiglottis only, IV – other (SAD cuff, pharynx, others)
FOI: Time to view carina: time from insertion of scope into the SAD lumen ending with visualization of the carina
FOI: Total intubation time (from insertion scope through SAD until 1st capnography trace is obtained)
No of attempts at intubation
Operator's visual analogue score: 0 to 10 (0 being very difficult, 10 being very easy)
Difficulty observed: tube rotation, tube impingement, failure to intubate
Surgery:
Duration of surgery in minutes

### LIST OF ABBREVIATIONS

CI	Chief Investigator
GCP	Good Clinical Practice
ICF	Informed Consent Form
ICH	International Conference on Harmonisation of technical requirements for registration of pharmaceuticals for human use.
ISF	Investigator Site File
NHS R&D	National Health Service Research & Development
NIMP	Non-Investigational Medicinal Product
PI	Principal Investigator
PIS	Participant Information Sheet
QA	Quality Assurance
QC	Quality Control
RCT	Randomised Control Trial
REC	Research Ethics Committee
SAE	Serious Adverse Event
SAD protector)	Supraglottic Airway device (Igel and LMA
SOP	Standard Operating Procedure
SSI	Site Specific Information
SUSAR	Suspected Unexpected Serious Adverse Reaction
TMF	Trial Master File

## STUDY PROTOCOL

### **Fibre-optic guided tracheal intubation through supraglottic airway devices – a randomised comparison between I-gel® and the LMA Protector™**

#### **1. INTRODUCTION**

Intubation through supraglottic airway devices (SAD) is a well-established technique in the management of patients with difficult airway. The passage of the endotracheal tube into the trachea using the SAD as a conduit can be performed blindly or with the use of a fiberoptic scope to guide intubation. The recently-published “Difficult Airway Society guidelines for management of unanticipated difficult intubation in adults” strongly emphasise the importance of minimising the number of airway interventions during a difficult airway scenario [1]. Hence, it is recommended that blind technique, with its lower success rate should no longer be used. In a patient where tracheal intubation is planned and when the initial plan (plan A) fails guideline recommends declaring the failure and moving on to plan B. Plan B involves securing the airway using a second a SAD. Guideline recommends use of second generation SAD due to added benefit of minimising gastric aspiration. Once the situation is stable, tracheal intubation can be performed through SAD using fiberoptic scope (camera device).

There are two second generation supraglottic airway devices, currently available: I-gel® and LMA Protector™ that allow tracheal intubation.

The I-gel is a second generation supraglottic airway device widely used in anaesthesia and resuscitation. Fiberoptic intubation through the I-gel has been evaluated in a recent prospective study, with the first attempt success rate of 91.4% (Taxak). In another study of patients with predicted difficult airway the success rate of the procedure at first attempt was 96%. (Kleine-Brueggeney)

LMA Protector is a recently introduced improved version LMA supreme another second generation supraglottic airway device. LMA supreme has been used in clinical practice for more than 10 years. But tracheal intubation through LMA supreme was extremely difficult because of the smaller breathing channel. Hence the improvised version has larger breathing channel. Compared to I-gel, this has larger gastric drainage tube and allows easy suction in the event of regurgitation. Therefore, in preventing the aspiration risk, LMA protector device appears to be superior to I-gel.

We are not aware of any study comparing these two devices for fiberoptic (camera) assisted tracheal intubation.

Comparing the efficacy of these devices in adults could in future guide the anaesthetists' choice of the SAD used in the difficult airway scenario, and also help the anaesthetists take informed decisions when using SADs to intubate the trachea in elective settings.

#### **2. RATIONALE**

##### **2.1 Aims and hypothesis**

The aim of this study is to compare the fiberoptic guided tracheal intubation through I gel supraglottic airway to that of LMA protector supraglottic airway device. Our hypothesis is that intubation through I – gel is easier and quicker.

Justification

The recently-published "Difficult Airway Society guidelines for management of unanticipated difficult intubation in adults" strongly emphasise the importance of minimising the number of airway interventions during a difficult airway scenario. When the initial plan (Plan A) of tracheal intubation (process of placing the breathing tube in to the wind pipe using initial method) fails, one should move on to plan B. Plan B involves placing supraglottic airway device and maintaining oxygenation. Once the oxygenation is stable, further attempt at intubation can be performed through the supraglottic airway device using fiberoptic scope. Supraglottic Airway Device-a type airway tube placed in the oral cavity (oropharynx) is used as conduit for passing the camera known as fiberoptic scope. Once the fiberoptic scope is placed in the wind pipe, the tracheal tube is railroaded over the fiberoptic scope.

DAS guidelines recommend to use second generation supraglottic airway device. The key feature of second generation supraglottic airway device is the ability to minimise the risk of aspiration.

The I-gel is a second generation supraglottic airway device widely used in anaesthesia and resuscitation. LMA Protector is a recently introduced improved version LMA supreme another second generation supraglottic airway device. LMA supreme has been used in clinical practice for more than 10 years. But tracheal intubation through LMA supreme was difficult because of the smaller breathing channel. Hence the improvised version has larger breathing channel. The LMA protector has a larger breathing channel and hence can be used a conduit for tracheal intubation. Compared to I-gel, LMA protector has a larger gastric drainage tube and allows easy suction in the event of aspiration. Therefore, in preventing the aspiration risk, LMA protector device appears to be superior to I-gel.

The data comparing the efficiency of fibre-optic guided intubation using the above supraglottic airway devices in adults are so far lacking. Comparing the efficacy of these devices in adults could in future guide the anaesthetists' choice of the supraglottic airway device used in the difficult airway scenario, and also help the anaesthetists take informed decisions when using SADs to intubate the trachea in elective settings.

## 2.3 Assessment and management of risk

Supraglottic airway device routinely used in clinical practice as an airway during general anaesthesia involving minor surgery. For this study patients requiring general anaesthesia and tracheal intubation will be selected. We do not anticipate any additional risks or benefits to the study participants. During the process of intubation, peripheral oxygen saturation is closely monitored.

## 3 OBJECTIVES AND OUTCOME MEASURES/ENDPOINTS

### 3.1 Primary objective

The aim of the study is to establish which of the two Supraglottic Airway Devices (a type airway tube placed in the oral cavity) is best suited for tracheal intubation (the process of placing the breathing tube in to the wind pipe). The process of placing the breathing tube is guided using fibre-optic scope (a camera device) through the Supraglottic Airway Device. The primary outcome of this will be time to complete the intubation.

Supraglottic Airway Device (a type airway tube placed in the oral cavity/oropharynx) is used as conduit for passing the camera (known as fiberoptic scope) to the wind pipe. Once the fiberoptic scope is placed in the wind pipe, the tracheal tube is railroaded over the fiberoptic scope and fiberoptic scope is removed. The breathing tube is then connected to the anaesthetic machine.

### 3.2 Secondary objectives

The results of the study should reveal whether there is a significant difference in the ease of intubation (the process of placing the breathing tube in to the wind pipe) and success rate between two supraglottic airway devices.

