### 3.3 Primary endpoint/outcome

Time to successful tracheal intubation: defined as the duration of time from insertion of scope through the supraglottic airway device, ending with the observation of a first square wave end-tidal capnography trace.

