### 3.4 Secondary endpoints/outcomes

- Number of attempts at the SAD placement
- SAD insertion time: defined as the duration of time SAD picked up in the hand, ending with the observation of a first square wave end-tidal capnography trace.
- Number of attempts at tracheal intubation
- The ease of placement of the SAD; 1-easy, 2 – mild difficulties, 3 – difficult, 4 - failure
- The fiberoptic quality of the laryngeal view (seen through the SAD) will be assessed, according to the previously published system, as: grade I – full view of the vocal cord, II – partial view of the vocal cords including arytenoids, III – epiglottis only, IV – other (SAD cuff, pharynx, others) (Joffe 2011)
- Time to carinal view: defined as the duration of time from insertion of scope into the SAD lumen ending with visualization of the carina.
- The number and type of airway manoeuvres performed during tracheal intubation
- Peri-operative complications

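### Does the intubation success rate named in section 3.2 need its own defined endpoint in section 3.4?

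*Combined protocol and SAP*

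**What the plan says.** The Trial Summary gives "Successful tracheal intubation" as the primary objective and pairs it with a time from scope insertion to end-tidal carbon dioxide. Its secondary row has "Successful placement of supra-glottic airway device" and does not mention intubation success. Section 3.1 names the time to complete intubation as the primary outcome. Section 3.3 defines that time as "ending with the observation of a first square wave end-tidal capnography trace".

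Section 3.2 has two secondary objectives: ease of intubation and the "success rate between two supraglottic airway devices". Section 3.4 includes "Number of attempts at tracheal intubation", manoeuvres, laryngeal view, time to carinal view and complications. Its only scale with a failure category is "The ease of placement of the SAD", which concerns the airway device and not the tracheal tube.

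Table 1 (Schedule of Observations) records the number of intubation attempts, has an item for failed intubation among the difficulties observed, and includes an operator visual analogue score. Section 7.6 also lists that score, as a rating of how easy the procedure was.

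The Introduction cites two I-gel results as background: a "first attempt success rate of 91.4" per cent, and a second study in which "the success rate of the procedure at first attempt was 96" per cent.

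**The concern.** A stated objective normally has a listed endpoint, and this one has none. The primary time ends at a capnography trace, so it exists only for patients who are intubated and cannot itself show a success rate. A count of attempts does not separate a patient intubated on the second attempt from one in whom intubation was abandoned after two.

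That leaves two open choices: first-attempt or overall success, and all randomised patients or only those with a placed airway device. If the choice were made after the data were seen, the more favourable answer could be picked. A reader of the Trial Summary might also take success to be primary, while a reader of 3.2 takes it as secondary. Ease of intubation looks similarly stranded, because the visual analogue score is not in the 3.4 list.

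**Working it through.** **Is there a conflict over the primary outcome?** Set side by side, the Trial Summary measures its primary objective by a time, 3.1 names a time, and 3.3 defines a time to successful intubation. All three agree. The objective in the Trial Summary reads as shorthand for the 3.3 endpoint.

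**Can success be derived from what is collected?**
- First-attempt success: one attempt and no failed-intubation entry.
- Overall success: no failed-intubation entry, or equivalently a capnography trace as in 3.3.
- Device placement failure: score 4 on the placement scale, which identifies the patients on whom the two denominators differ.

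Nothing is missing from the data. Ease of intubation is likewise a named assessment in 7.6.

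**How much could the definition matter?** The plan has no figure to reproduce here: it gives no success rate for the LMA Protector, no share of later successes and no placement failure rate. All counts below are assumptions. The arms have 180/2 = 90 patients each (Trial Summary; 1:1 in 7.3). The leading arm has 86/90 = 95.6% or 82/90 = 91.1%, close to the two cited I-gel rates. The trailing arm is a free choice.

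Overall successes = first-attempt successes + r × first-attempt failures, rounded to whole patients with halves up, where r is the share who succeed later. Tests are two-sided Fisher exact, with Newcombe 95% intervals.

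| r | Successes of 90 | Difference, points (95% CI) | p |
|---|---|---|---|
| 0 (first attempt) | 86 v 76 | 11.1 (2.3 to 20.4) | 0.023 |
| 0.20 | 87 v 79 | 8.9 (0.9 to 17.5) | 0.048 |
| 0.25 | 87 v 80 | 7.8 (-0.0 to 16.2) | 0.081 |
| 0.50 | 88 v 83 | 5.6 (-1.2 to 13.1) | 0.17 |
| 0.75 | 89 v 87 | 2.2 (-3.2 to 8.3) | 0.62 |

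Starting from 82 v 70 (13.3 points, p=0.022), the p values for r = 0.20, 0.25, 0.50 and 0.75 are 0.039, 0.061, 0.16 and 0.44.

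In the table, the step from p=0.048 to p=0.081 is one patient in the trailing arm (79 v 80). The gap shrinks as r grows because later success helps the arm with more failures. That is a real difference between two quantities, and reporting both would show it.

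**Denominator.** Take 86 v 76 first-attempt successes and leave out patients whose device placement failed:

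| Left out, leading v trailing arm | Comparison | p |
|---|---|---|
| 0 v 2 | 86/90 v 76/88 | 0.038 |
| 2 v 2 | 86/88 v 76/88 | 0.010 |
| 2 v 4 | 86/88 v 76/86 | 0.017 |
| 0 v 3 | 86/90 v 76/87 | 0.061 |
| 0 v 4 | 86/90 v 76/86 | 0.098 |
| 1 v 6 | 86/89 v 76/84 | 0.12 |
| 0 v 6 | 86/90 v 76/84 | 0.24 |

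The denominator matters only if there are several placement failures and they fall mainly on one device.

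**The case for a change.** The strongest case for a change is that several rates can be derived, so one should be fixed in advance. The same patients could give p=0.023 on one fair reading of 3.2 and p=0.17 on another, and 3.2 asks specifically about a significant difference. The contents list names a statistics section, but the available text has none to settle the matter. Writing down a definition would cost only a few lines and need no new data.

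Part of this stands. Section 3.2 does name a rate that 3.4 neither lists nor defines, and the arithmetic is right. Three things limit its weight:

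- The change of conclusion comes from starting gaps placed near p=0.02 and then watching 0.05 being crossed, with no document figure for one of the two arms.
- The precedents the protocol cites are first-attempt rates, so the natural lead reading is visible, with overall success beside it.
- Listing the rate in 3.4 would leave overall success partly open, because the available text sets no maximum number of attempts and no criterion for failure. It would also not alter how failed intubations enter the primary time, which is a separate question.

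The participant flow chart is not reproduced in the available text and may show what follows a failed placement, so the silence on the denominator is certain only for the visible text.

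**Conclusion.** No change is called for. What remains is a gap in wording for a secondary comparison: success rate is an objective in 3.2 without an entry in 3.4. Time is the primary outcome wherever the protocol states one. The variables for first-attempt and overall success, and for both denominators, are already collected. A competent analyst would report first-attempt and overall success with intervals and state the denominator.

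In the 86 v 76 illustration the choice of rate moves the difference from 11.1 points to between 8.9 and 2.2 points for r from 0.20 to 0.75. The same device leads throughout, and whether p lies below 0.05 depends on invented counts. The conclusion assumes that attempts and failed intubations are recorded as Table 1 sets out, and that the report does not show one success rate without the other. It would be weaker if placement failures proved numerous and one-sided.

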### 3.3 Primary endpoint/outcome

Time to successful tracheal intubation: defined as the duration of time from insertion of scope through the supraglottic airway device, ending with the observation of a first square wave end-tidal capnography trace.

### 3.4 Secondary endpoints/outcomes

- Number of attempts at the SAD placement
- SAD insertion time: defined as the duration of time SAD picked up in the hand, ending with the observation of a first square wave end-tidal capnography trace.
- Number of attempts at tracheal intubation
- The ease of placement of the SAD; 1-easy, 2 – mild difficulties, 3 – difficult, 4 - failure
- The fiberoptic quality of the laryngeal view (seen through the SAD) will be assessed, according to the previously published system, as: grade I – full view of the vocal cord, II – partial view of the vocal cords including arytenoids, III – epiglottis only, IV – other (SAD cuff, pharynx, others) (Joffe 2011)
- Time to carinal view: defined as the duration of time from insertion of scope into the SAD lumen ending with visualization of the carina.
- The number and type of airway manoeuvres performed during tracheal intubation
- Peri-operative complications

## 4 TRIAL DESIGN

Multi-centre randomised-controlled trial

## 5 STUDY SETTING

The study will be conducted in 2 hospitals in England. University Hospitals Coventry & Warwickshire NHS Trust and Oxford University Hospitals.

## 6 ELIGIBILITY CRITERIA.

### 6.1 Inclusion criteria

All patients aged above 18, presenting for elective surgical procedure, where a supraglottic airway device can be used and left in place throughout the duration of surgery and requiring tracheal intubation will be invited to take part in the study. This involves a group of patients presenting for abdominal surgery and peripheral limb operation where tracheal intubation is indicated.

### 6.2 Exclusion criteria

- Patients who are do not want to take part or do not give consent
- Patients with class II obesity (BMI >40)
- Patients below 18 years of age
- ASA 3, 4 and 5,
- Patients with mouth opening of less than 3 cm

- Patients deemed to require awake intubation
- Surgery involving head and neck region
- Surgery requiring prone position

## 7 TRIAL PROCEDURES

The suitable patients for the study will be screened from the operating theatre list. During the preoperative assessment one of the investigator or co-investigator will provide patient information sheet. Patients will be given adequate time to read the information and any questions will be answered. If they are satisfied and willing to take part in the study, written consent will be obtained.

### 7.1 Recruitment

Both Chief investigator and co-investigators identify the suitable operating list. Then the suitable patients will be identified based on the scheduled surgical procedure. Only those patients meeting the inclusion criteria will be approached.

#### 7.1.1 Patient identification

The patients undergoing surgery that requires tracheal intubation are suitable to be included in the study. Based on the scheduled surgery on the operating list, the suitable patients will be identified. During the preoperative assessment one of the investigator or co-investigator will provide patient information sheet. Patients will be given adequate time to read the information and any questions will be answered. If they are satisfied and willing to take part in the study, written consent will be obtained.

### 7.2 Consent

Participants will be given enough time to read the patient information leaflet (minimum of 2 hours). Once they have read the information, any questions will be answered. If they agree for the study, they will be asked to complete the consent form. The consent will be obtained by chief investigator, coinvestigator or one of the research team member, supervised by one of the investigator.

### 7.3 Randomisation scheme

Randomisation for this study will be completed on a 1:1 basis via sealed envelopes. The Statistician will create 2 master randomisation lists for each site and the envelopes will be numerically ordered.

On arrival to the anaesthetic room, sealed envelope will be opened to reveal the group. Based on the group, following induction of general anaesthesia, the chosen supraglottic airway device will be inserted. Once the supraglottic airway device placement confirmed, tracheal intubation is completed using Fiberoptic scope.

The randomisation will determine which supraglottic airway device to choose. Rest of the process is similar in both groups.

In theatre once the envelopes have been opened the randomisation log will need to be completed. The envelopes containing the assigned device will be retained in a folder in theatre.

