### 7.5 Baseline data

Base line data includes gender, age, weight, height, BMI & ASA score

Airway assessment includes Mallampati score, thyromental distance, mouth opening and neck movement

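### Site and baseline airway measures have no stated role in comparing intubation time, and the primary endpoint has no value for failed patients, so an analysis of times alone drops randomised patients

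*Combined protocol and SAP*

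**What the plan says.** The Trial Summary plans "180 across 2 sites", and section 5 confirms two hospitals. Section 7.3 states "Randomisation for this study will be completed on a 1:1 basis via sealed envelopes" and then "The Statistician will create 2 master randomisation lists for each site and the envelopes will be numerically ordered". It does not mention blocking. Section 7.5 lists demographics including BMI and ASA score, and adds "Airway assessment includes Mallampati score, thyromental distance, mouth opening and neck movement".

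The primary endpoint (3.3) runs from insertion of the scope through the device to the first square-wave capnography trace, and is named as a time to successful intubation. The Schedule of Observations also has a difficulty field with the entries "tube rotation, tube impingement, failure to intubate". It scores device placement from 1 to 4, where 4 is failure; section 3.4 repeats that scale. Under 7.3 the envelope is opened on arrival in the anaesthetic room, and the scope is used only after device placement is confirmed.

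No section names a test or model for intubation time, a role for site or any baseline measure, or a value or rank for a failure. The list of contents announces a section on statistics and data analysis. In the body, section 6 is eligibility, and section 7 (procedures) is followed by section 8 (data handling).

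**The concern.** Two separate matters are involved.

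**Precision.** If the lists are made by site, the analysis would normally reflect site. If baseline airway measures predict intubation time, using them narrows the interval at no cost in patients. Covariates chosen after the times have been seen are open to challenge, so they need naming beforehand.

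**Validity.** A patient recorded as a failed intubation has no endpoint time. A patient whose device placement fails may never have the scope inserted, so the clock never starts. Both failures occur after randomisation and may depend on the device. A comparison of available times leaves these patients out. A device that fails more often could then look as good as, or better than, its comparator.

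**Working it through.** **Inputs from the protocol.** 180 patients, 1:1, so 90 per arm; two sites. No alpha, power, effect, SD, site effect, R² or failure rate is given for this trial, so 180 cannot be reproduced. Assumed throughout: two-sided 5%, equal sites. As a benchmark, 90 per arm detects (1.960 + 0.842) × √(2/90) = 0.418 SD at 80% power.

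**1. Ignoring site.** Let s be the share of variance due to site and k = 1/√(1 − s). Compare with a site-adjusted test at 80% power.
- Lists blocked within site: type I error = 2[1 − Φ(1.96k)]; power = 1 − Φ(1.96k − 2.80).
- Not blocked: type I error stays at 5%; power = 1 − Φ(1.96 − 2.80/k).

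| s | k | Type I, blocked | Power, blocked | Power, unblocked |
|---|---|---|---|---|
| 0 | 1.000 | 5.0% | 80.0% | 80.0% |
| 2% | 1.010 | 4.8% | 79.4% | 79.2% |
| 6% | 1.031 | 4.3% | 78.2% | 77.5% |

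The loss is 0 to 1.8 points if blocked and 0 to 2.5 if not. A blocked but unadjusted test is conservative.

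**2. Site plus three covariates on log time.** With no failures, the ratio of adjusted to unadjusted interval width is close to 1.009 × √(1 − R²), where 1.009 is the price of the extra terms. Simulation (3,000 runs per cell, true effect 0.42 SD, failures unrelated to covariates, failures and any longer times set to 2.5 SD above the mean) gave:

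| R² | No failures | 4% failures | 8.6% failures |
|---|---|---|---|
| 0 | 1.009 | 1.009 | 1.008 |
| 0.05 | 0.983 | 0.989 | 0.994 |
| 0.10 | 0.958 | 0.967 | 0.977 |
| 0.20 | 0.902 | 0.925 | 0.943 |

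**3. Site-stratified rank test (van Elteren) against a plain rank test, failures ranked last in both.** Simulated gain (4,000 runs per cell, failures of 4% or 9%): −0.6 to 0 points at s = 0, 0.1 to 0.7 at s = 2%, and 1.8 to 2.3 at s = 6%. The Monte Carlo standard error is about 0.7 points on each power, so the gain at 2% is barely distinguishable from none.

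**4. What the failure rule costs when failures are equal in the arms.** For a rank test, power ≈ Φ(Δ/SE − 1.96), with SE = √[(2n + 1)/(12n²)]. For a 0.42 SD shift, Δ = Φ(0.42/√2) − 0.5 = 0.117 if failures are dropped, with n = 90(1 − f). If failures are ranked last, Δ = (1 − f)² × 0.117 with n = 90.
- f = 4%: dropped, 0.1168/0.0440 = 2.65, power 76%. Ranked last, 0.1076/0.0432 = 2.49, power 70%.
- f = 9%: dropped, 0.1168/0.0452 = 2.58, power 73%. Ranked last, 0.0967/0.0432 = 2.24, power 61%.

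Simulation gives 76% to 70% and 75% to 63%. The cost is about 6 and 12 points.

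**5. What the failure rule protects against.** Suppose times do not differ but failure rates do. Dropping failures rejects about 5% of the time. Ranking them last gives Δ = (difference in failure rates)/2.
- 4% v 15%: 0.055/0.0432 = 1.27; rejection about 25%.
- 4% v 8.6%: 0.023/0.0432 = 0.53; rejection about 8% (9% in simulation).

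If the slower device also fails more often, the cost in step 4 reverses. With times 18% longer (log SD 0.4) and failures of 4% v 8.6%, simulated power was 76% with failures dropped and 83% with them ranked last.

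**6. Scale of failures.** The Introduction cites other I-gel studies: "with the first attempt success rate of 91.4" and "the success rate of the procedure at first attempt was 96" (both percentages). Applied to 90 patients these give 90 × 0.086 = 7.7 and 90 × 0.04 = 3.6 first-attempt failures.

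**The case against.** The strongest objection is that this is one line of a larger gap. With no analysis text at all, the choice of covariates is secondary, and no section shows that Mallampati score, mouth opening or BMI predicts time for scope-guided intubation through these devices. The exclusions in 6.2 (small mouth opening, high BMI, ASA 3 to 5, awake intubation, head and neck surgery) make low R² values plausible. This stands, and it is why the precision part is called modest and may be nil.

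A second objection is that ranking failures last is not free and answers a different question: a composite of failure and time, rather than time among those intubated. This also stands; step 4 shows the cost. The case for the rule is that it keeps the randomised groups intact.

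Several stronger readings are tempting but not supported:
- That the sponsor plans a plain two-group test. No test is stated.
- That ignoring site or covariates would bias the result or inflate type I error. If every patient has a time, it would not.
- That the cited 91.4% and 96% bound the failures here. They are first-attempt rates for I-gel in other studies, one in predicted difficult airways. Later attempts may succeed, this trial may differ, and no LMA Protector figure is given.
- That the list wording implies a second stratification factor. One list per site is a natural reading of "The Statistician will create 2 master randomisation lists for each site and the envelopes will be numerically ordered", and a second list could be a reserve.

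**Conclusion.** The point holds, in two parts of unequal weight. The more important part is that the primary endpoint is undefined for failed intubations and may be undefined for failed device placements, with no rule for including them. Dropping them can hide a device difference: under assumed failures of 4% v 15% and equal times, the chance of detecting any difference is about 5% instead of about 25%. Including them costs about 6 to 12 power points if failures are equal at 4 to 9%, so the rule should be presented as a validity measure and not as a gain in precision.

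The lesser part is that site and the collected baseline measures have no stated role. Using them is worth 0 to 2.5 power points for site shares of 0 to 6%. For R² of 0 to 0.20 the interval changes from about 1% wider to 10% narrower, and the narrowing is smaller once failures are included. All these sizes rest on assumed site shares, R² and failure rates. The list wording and the silence on blocking are minor points of clarity.

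**What to change.** State the primary comparison in advance, in all randomised patients by allocated device, in one of two forms:
- A site-stratified rank test such as van Elteren, with failed intubations and failed device placements ranked as the longest times. It needs no numerical value for failures but leaves out the covariates.
- A linear model on log time with site and a few named baseline covariates (for example Mallampati score, mouth opening and BMI), and a value for both kinds of failure fixed before any times are seen.

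In either case, say which recorded events count as failures for the analysis, and report their number by arm beside the primary result. In 7.3, say whether there is one list per site or two at each site, and whether the lists are blocked.

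The cost is a few sentences and no new data. The downsides are an interval about 1% wider if site and covariates explain nothing, the power cost in step 4 if failures are equal, and, for the log-time model, dependence on the chosen failure value.
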